1 INTRODUCTION

This document describes the statistical analysis for protocol VIB4920.P2.S2, a Phase 2 randomized, double-blind, placebo controlled, proof of concept study to evaluate the efficacy and safety of VIB4920 in subjects with Sjögren's Syndrome (SS). The study will enroll 2 SS populations. Population #1 will be composed of subjects with moderate to severe systemic disease activity defined by European League Against Rheumatism (EULAR) Sjögren's Syndrome Disease Activity Index (ESSDAI) \geq 5. Population #2 will be composed of subjects with moderate to severe subjective symptoms defined by EULAR Sjögren's Syndrome Patient Reported Index (ESSPRI) score \geq 5 and residual stimulated salivary flow but with mild systemic disease activity defined by ESSDAI score < 5.

2 STUDY OVERVIEW

2.1 Study Objectives and Endpoints

The objectives and corresponding endpoints are listed in Table 1 below:

Primary objective	Endpoints/variables	
• Population #1: To evaluate the clinical efficacy of multiple doses of VIB4920 in glandular and extraglandular manifestations of SS patients with moderate to high systemic disease activity	• Population #1: Change from baseline in ESSDAI at Day 169	
• Population #2: To evaluate the clinical efficacy of multiple doses of VIB4920 in the key subjective complaints of SS (dryness, fatigue, pain)	• Population #2: Change from baseline in ESSPRI at Day 169	
Secondary objectives	Endpoints/variables	
 Population #1: To evaluate the effect of VIB4920 on systemic activity and patient-reported outcomes in subjects with SS 	 ESSPRI ESSDAI[3] and ESSDAI[4] response Functional Assessment of Chronic Illness Therapy (FACIT)-Fatigue Ocular Surface Disease Index (OSDI) Patient's Global Impression of Severity (PGIS) 	
• Population #2: To evaluate the effect of VIB4920 on patient-reported outcomes in subjects with SS	 ESSPRI response FACIT-Fatigue OSDI PGIS 	
• Population #1 & #2: To evaluate the safety and tolerability of multiple doses of VIB4920 in subjects with SS	• Incidence of treatment emergent adverse events (TEAEs), TE serious adverse events (TESAEs), TE adverse events of special interest (TEAESIs), and laboratory, vital sign, and electrocardiogram (ECG) abnormalities	

Table 1	Study	Objectives	and Endpoints
---------	-------	------------	---------------

Table 1Study Objectives and Endpoints

• Population #1 & #2: To characterize the pharmacokinetics (PK) of VIB4920 in subjects with SS	• Drug concentration and PK parameters
• Population #1 & #2: To assess the immunogenicity of VIB4920 in subjects with SS	• Anti-drug antibodies (ADA)
Exploratory objectives (Population #1 & #2)	Endpoints/variables

2.2 Study Design

2.2.1 Overview

This is a randomized, double-blind, placebo-controlled, parallel-arm study to evaluate the efficacy, safety, and tolerability of VIB4920 in adult subjects with SS, diagnosed according to the 2016 American College of Rheumatology (ACR)/EULAR Criteria. The study will enroll 2 SS populations as defined in section 1 INTRODUCTION. Within each population,

eligible subjects will be randomized to receive VIB4920 1500 mg or placebo intravenously (IV) once every 2 weeks x 3 doses, then once every 4 weeks (Q4W) for 4 additional doses (Stage I). Randomization will be stratified by ESSDAI score at screening (< 10 points vs \geq 10 points) for Population #1 and by ESSPRI score at screening (< 7.5 points vs \geq 7.5 points) for Population #2. Starting on Day 169, subjects randomized to VIB4920 will receive placebo Q4W for 5 doses and subjects randomized to placebo will receive VIB4920 Q4W for 5 doses (Stage II). Subjects who had investigational product (IP) discontinuation will not be eligible for treatment during Stage II. All subjects will be followed for at least 12 weeks after their last dose of IP administration.

A study schematic is presented in Figure 1.

Figure 1Study Flow Diagram

2.3 Sample Size

Population #1: The planned sample size of 72 subjects (36 subjects in the VIB4920 group and 36 subjects in the Placebo group) will provide 80% power to detect a difference in mean change from baseline to Day 169 in ESSDAI of 3.0 (assumed standard deviation of 5) between the VIB4920 and placebo treatment groups at a two-sided alpha level of 0.10 using 2-sample t-test. The minimum detectable difference is 2.0 between the 2 treatment groups. The estimated standard deviation of 5 is based on the published results (Mariette et al, 2015; Fisher et al, 2017) and internal data.

Population #2: The planned sample size of 102 subjects (51 subjects in the VIB4920 group and 51 subjects in the Placebo group) will provide 80% power to detect a difference in mean change from baseline to Day 169 in ESSPRI of 1.0 (assumed standard deviation of 2) between the VIB4920 and placebo treatment groups at a two-sided alpha level of 0.10 using 2-sample t-test. The minimum detectable difference is 0.66 between the 2 treatment groups. The estimated standard deviation of 2 is based on the published results (Mariette et al, 2015; Fisher et al, 2017) and internal data.

3 STATISTICAL METHODS

3.1 General Considerations

All statistical calculations will be primarily performed using SAS[®] System Version 9.4 or higher. Categorical data will be summarized by the frequency counts and percentage of subjects in each category. Continuous variables will be summarized by descriptive statistics, including number of observations, mean, standard deviation, median, first quartile, third quartile, minimum, and maximum.

3.1.1 Definition of Baseline

Unless otherwise specified, baseline will be defined as the last non-missing valid observation prior to the first administration of IP. In cases where baseline measurements are taken on the same day as IP and no times are reported, it will be assumed that these measurements are taken prior to IP being administered.

3.1.2 Analysis Windows

Analysis visit windows will be used for all visit-based assessments to map longitudinal observations to scheduled visits and thereby allow for by-visit analyses, since not all assessments are performed on the scheduled day. Unless otherwise specified, all longitudinal efficacy and safety data analyses will be based on the analysis visit windows. The analysis visit windows will be calculated by bisecting the interval between adjacent scheduled visit days except for the first post-treatment visit and Day 169 visit. The first post-treatment visit will start at Day 2. When slotting visits to the Day 169 window, this should only occur for assessments on or before the date of the nominal Day 169 dose. Assessments after this date should be slotted to the following visit window. The detailed analysis visit windows will be specified in the statistical programming plan (SPP).

The actual assessment day will be mapped to the windows defined for each scheduled study visit with following rules:

- If more than one assessment falls within a visit window, the closest non-missing assessment to the scheduled day will be used in the analysis.
- If 2 non-missing assessment actual dates are equidistant from the target day, the later visit will be used in the analysis.
- For retest values of laboratory data, the retest value (the last valid observation assessed on the same visit day) will be chosen.

3.2 Protocol Deviations

All protocol deviations will be classified as either major protocol deviations or minor protocol deviations. The major protocol deviations are considered as the important protocol deviations, which may significantly impact the completeness, accuracy, and/or reliability of the study data, and may significantly affect a subject's rights, safety, or well-being. All the protocol deviations will be listed, and the major protocol deviation will be summarized. Some classifications of major protocol deviations are listed below.

- Did not meet inclusion criteria or met exclusion criteria.
- Blindness of treatment assignment was broken by site investigator before Day 169
- Received prohibited concomitant medication
- Serious breach of good clinical practice

The list may be updated and will be finalized and documented prior to the database lock for the interim analysis.

3.3 Analysis Sets

3.3.1 Full analysis set

The full analysis set includes all randomized subjects who received any dose of IP. Subjects will be analyzed according to the treatment randomized. The efficacy analysis will be based on the full analysis set.

3.3.2 Safety analysis set

The safety analysis set includes all subjects who received any dose of IP. Subjects will be analyzed according to the treatment that they actually received. The safety and ADA analyses will be based on the safety analysis set.

If subjects who are randomized to placebo receive any dose of VIB4920 in Stage I of the study, the treatment actually received will be VIB4920 for the subjects.

3.3.3 Pharmacokinetics analysis set

The PK analysis set includes all subjects who received IP and have at least one quantifiable plasma PK observation post-first dose. Subjects will be analyzed according to the treatment that they actually received. PK analyses will be based on the PK analysis set.

3.3.4 Cross-over analysis set

The cross-over analysis set includes all subjects who received any dose of IP during Stage II of the study.

3.3.5 Any VIB4920 analysis set

The any VIB4920 analysis set includes all subjects who received at least one dose of VIB4920 during the study.

3.4 Study Subjects

3.4.1 Subject Disposition

A summary of subject disposition will be presented using the categories presented below.

• Screened

- Screen failed with reasons
- Randomized
- Randomized but not treated
- Randomized and treated
- Completed Stage I treatment
- Completed treatment
- Discontinued treatment with reasons
- Completed Stage I
- Completed study
- Discontinued study with reasons

3.4.2 Demographics, Baseline Characteristics, and Medical History

The demographics (age, gender, race, ethnicity, height, weight, and body mass index) will be summarized by treatment group and overall for the full analysis set.

A summary of baseline disease characteristics, by treatment group and overall for the full analysis set will include

- Baseline ESSDAI total score descriptive statistics
- Baseline ESSDAI total score (< 10 points vs \ge 10 points) n (%)
- Baseline ESSPRI total and component score descriptive statistics
- Baseline ESSPRI total score (< 7.5 points vs \geq 7.5 points) n (%)
- Baseline OSDI descriptive statistics descriptive statistics
- Schirmer's test $\leq 5 \text{ mm in at least 1 eye n (%)}$
- Time (years) from initial diagnosis to randomization descriptive statistics
- Positive SS-A/SS-B at baseline n (%)
- Baseline RF auto-antibody levels: descriptive statistics
- Stimulated salivary flow at baseline descriptive statistics
- Concomitant RA or SLE n (%)

Significant medical history finding will be summarized by MedDRA system organ class (SOC) and preferred term (PT) by treatment group and overall for the full analysis set.

3.4.3 Investigational Product Exposure

The number of doses received, amount (mg) of the IP received, durations of the IP exposure, and total subject years exposure will be summarized by treatment. This summary will be produced for the Stage I and Stage II separately using the safety analysis set and cross-over analysis set respectively, and for the overall study using any VIB4920 analysis set.

- Duration of the IP exposure is defined as follows
 - Stage I: minimum of (date of last dose before Day 169 + 28 first dose date) and (Day 169 date first dose date)
 - Stage II: last dose date + 28 Day 169 date + 1
 - Overall study using any VIB4920 analysis set: duration of exposure to VIB4920 in the study
- The amount (mg) of IP: if a subject received partial dose at a dosing visit, then the amount of IP at that dosing visit will be estimated based on the actual volume administered.
- Treatment compliance for an individual subject = (Total number of doses received)/ (Total number of doses planned per protocol) ×100%.

3.4.4 Prior and Concomitant Medications

Number (%) of subjects who receive prior medications and concomitant medications during Stage I and during Stage II + Off-treatment follow-up period will be summarized by world health organization (WHO) Drug dictionary Anatomical Therapeutic Chemical (ATC) category and PT. At each level of summarization, a subject is counted once if he/she reported one or more medications at that level. The summary of prior medications and concomitant medications during Stage I will be based on the safety analysis set. The summary of concomitant medications during Stage II + Off-treatment follow-up period will be based on the cross-over analysis set.

The prior and concomitant medications are defined as below.

- Prior medications are defined as medications with a stop date occurring before the first IP administration date.
- Concomitant medications during Stage I are defined as follows:
 - Medications with a start date before the Day 169 IP administration date and stop date on or after the first IP administration date for subjects entering Stage II.
 - Medications with a stop date on or after the first IP administration date for subjects not entering Stage II.

• Concomitant medications during Stage II + Off-treatment follow-up period are defined as medications with a stop date on or after the Day 169 IP administration date.

Use of disease-related medications at baseline, defined as all disease-related medications with an intake at the date of first dose of IP (ie, start date on or before the date of first dose and end date on or after date of first dose or ongoing) will be summarized for the full analysis set. The number and percentage of subjects who receive rescue medication during Stage I and during Stage II + Off-treatment follow-up period will also be summarized for the full analysis set and cross-over analysis set respectively.

Rescue medications for population #1 are listed below:

- Azathioprine (AZA) > 150 mg/day, methotrexate (MTX) > 20 mg/week, leflunomide >20 mg/day, mycophenolate mofetil (MMF) > 2gm/day OR any increase from baseline (including initiation of treatment)
- Any increase from baseline in anti-malarial (including initiation of treatment)
- Initiation of any new conventional disease-modifying anti-rheumatic drug (cDMARD)
- Oral prednisone > 10 mg/day OR any increase from baseline (including initiation of treatment)
- Intramuscular, IV, or intraarticular corticosteroids
- Corticosteroids with a long biologic half-life (eg, dexamethasone, betamethasone)

Rescue medications for population #2 are listed below:

- Oral, intramuscular, IV, or intraarticular corticosteroids
- MTX, AZA, leflunomide, MMF, and other cDMARD or immunosuppressive or antiproliferative medications
- Any increase from baseline in anti-malarial (including initiation of treatment)
- Any increase or initiation of new doses of cevimeline or pilocarpine and cyclosporine eye drops (Restasis)

The missing start/stop date of medications will be imputed as appropriate and the details of the imputation will be included in the SPP.

3.5 Efficacy Analyses

3.5.1 **Primary Efficacy Endpoint(s) and Analyses**

3.5.1.1 Primary efficacy endpoint

Population #1: The primary efficacy endpoint is change from baseline in ESSDAI at Day 169.

Population #2: The primary efficacy endpoint is change from baseline in ESSPRI at Day 169.

ESSDAI:

The ESSDAI is a validated consensus disease activity index that is able to capture changes in the severity of systemic manifestations of SS, with 12 domains, with associated weights as shown in Table 2.

Domain	Weight	Activity Levels
Constitutional	3	0-2
Lymphadenopathy	4	0-3
Glandular	2	0-2
Articular	2	0-3
Cutaneous	3	0-3
Pulmonary	5	0-3
Renal	5	0-3
Muscular	6	0-3
Peripheral Nervous System	5	0-3
Central Nervous System	5	0,2,3
Hematological	2	0-3
Biological	1	0-2

Table 2ESSDAI Domains, Weights and Activity Levels

The final score is calculated as follows:

Total Score = Sum of all 12 domain scores

Domain score = Activity level × Domain weight

The theoretical range of values for the ESSDAI is 0 to 123, with higher ESSDAI scores indicate more severe disease.

ESSPRI:

The ESSPRI is a 3-item, subject-completed assessment of SS symptoms. The instrument captures subject-rated severity of dryness, fatigue, and pain using 0-10 numeric rating scales anchored as no symptom (0) and maximal imaginable symptom (10). The recall period is stated in each question as "the last 2 weeks." The ESSPRI total score is the mean of the 3 items and is calculated as follows:

ESSPRI Total Score = (Dryness + Fatigue + Pain) / 3

3.5.1.2 Primary efficacy analysis

Population #1: The primary efficacy endpoint will be analyzed using the mixed-effect model for repeated measures (MMRM) approach based on Stage I data for the full analysis set. The

model will include fixed effects for treatment, visit, visit by treatment interaction, and baseline ESSDAI score.

Population #2: The primary efficacy endpoint will be analyzed using the MMRM approach based on Stage I data for the full analysis set. The model will include fixed effects for treatment, visit, visit by treatment interaction, and baseline ESSPRI score.

From the model, the estimated treatment effect (ie the difference (VIB4920 – placebo) in LSMeans) at Day 169 will be obtained, together with a two-sided 90% confidence interval (CI), standard error (SE) and p-value. The significance of treatment effect will be tested by using a two-sided test at significance level α of 0.1. Additionally, estimates of the LSMeans for each treatment group will be obtained, together with the associated SE.

Longitudinal presentations of results over time up to Day 169 based on the same analysis will be created.

Model assumptions for MMRM will be checked with graphical displays (residual plots and a quartile-quartile (Q-Q) plot). If the model assumptions are not met, appropriate data transformations or the non-parametric approaches will be used.

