3.5.1.5 Sensitivity analysis of primary efficacy endpoint

The sensitivity analysis will be performed for the primary efficacy endpoint using the same model as the primary analysis with the following handling plan for the rescue medication use and treatment discontinuation.

- Impute result after rescue medications using the worst score on or before Day 169 including baseline. Include data collected after discontinuation of study treatment.
- Include data collected after rescue medications and data collected after discontinuation of study treatment.

In addition, the primary efficacy endpoint will be analyzed based on the time adjusted area under the curve (AUC) of change from baseline. First, the AUC of the ESSDAI and ESSPRI score from baseline to Day 169 will be calculated using the trapezoidal rule. Second, the time adjusted AUC will be obtained by dividing the AUC by the total time for baseline. Third, time adjusted AUC of change from baseline will be calculated by subtracting the baseline score from the time adjusted AUC. All observed data including data collected after rescue medications will be used to calculate the time adjusted AUC. The time adjusted AUC of change from baseline will be analyzed using MMRM approach including fixed effects for treatment, visit, visit by treatment interaction, and corresponding baseline score.

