3.5.1.8 Additional analysis

The change from baseline in ESSDAI for population #1 and change from baseline in ESSPRI for population #2 will be analyzed for Stage II + Off-treatment follow-up period based on the cross-over analysis set using the same MMRM model as the primary analysis. Data collected after rescue medications and after discontinuation of study treatment will be included.

The change from baseline in modified ESSDAI excluding peripheral nervous system, central nervous system, and pulmonary domains for population #1 will be analyzed using MMRM approach for Stage I and Stage II + Off-treatment follow-up period based on the full analysis set and cross-over analysis set respectively. The model will include fixed effects for treatment, visit, visit by treatment interaction, and baseline modified ESSDAI score. The handling plan for rescue medication use and treatment discontinuation for Stage I analysis is the same as those for the primary (section 3.5.1.3) and sensitivity (section 3.5.1.5) analyses of the primary efficacy endpoint. Data collected after rescue medications and after discontinuation of study treatment will be included for the Stage II + Off-treatment follow-up period analysis.

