3.5.2.2 Secondary efficacy analysis

The continuous secondary efficacy endpoints of population #1 and population #2 will be analyzed based on Stage I data for the full analysis set using the MMRM approach, with treatment, visit, visit by treatment interaction, randomization stratification factor, and corresponding baseline value. Handling plan for the rescue medication use and treatment discontinuation will be the same as those described for the primary endpoints in sections 3.5.1.3 and 3.5.1.5.

The details of these analyses and presentations of results will be the same as those described for the primary endpoints in section 3.5.1.2.

The analysis for Stage II + Off-treatment follow-up period will be performed using the same MMRM approach based on the cross-over analysis set. Data collected after rescue medications and after discontinuation of study treatment will be included.

The binary secondary efficacy endpoints of population #1 and population #2 will be analyzed for the full analysis set using a logistic regression model, with treatment and corresponding baseline score included in the model.

The estimated treatment effect (ie, the odds ratio for VIB4920 versus placebo), corresponding 90% CI, and 2-sided p-value will be presented. In addition, the response rate and the corresponding 90% CI within each treatment group will be presented. Longitudinal presentations of results over time up to Day 169 will be created using full analysis set. In addition, the analysis will be produced for Stage II + Off-treatment follow-up period separately using the cross-over analysis set.

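### The primary MMRMs and the related ESSDAI/ESSPRI change models omit the randomization stratum that the continuous secondary MMRMs include; adding it is a minor improvement at almost no cost

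*SAP*

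**What the plan says.** SAP 2.2.1 and Protocol 4.1 stratify randomization by one two-level factor per population: screening ESSDAI <10 or ≥10 (Population #1), and screening ESSPRI <7.5 or ≥7.5 (Population #2).

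The models then differ in whether they carry that factor:

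- **Primary (SAP 3.5.1.2).** For Population #1 the "model will include fixed effects for treatment, visit, visit by treatment interaction, and baseline ESSDAI score". Population #2 has the same terms with baseline ESSPRI. No stratum.
- **Sensitivity (SAP 3.5.1.5).** The rescue-handling analyses are run "using the same model as the primary analysis". The time-adjusted AUC uses an "MMRM approach including fixed effects for treatment, visit, visit by treatment interaction, and corresponding baseline score". No stratum.
- **Additional (SAP 3.5.1.8).** The Stage II analysis of the primary scores reuses the primary model. For modified ESSDAI, "The model will include fixed effects for treatment, visit, visit by treatment interaction, and baseline modified ESSDAI score". No stratum.
- **Continuous secondary (SAP 3.5.2.2).** MMRM "with treatment, visit, visit by treatment interaction, randomization stratification factor, and corresponding baseline value". Stratum included.
- **Responder (SAP 3.5.2.2).** Logistic regression "with treatment and corresponding baseline score included in the model". No stratum.

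The SAP gives no reason for the difference. Protocol 10.5.1 names the MMRM but no covariates, so the SAP alone settles the matter. SAP 3.1.1 takes baseline as the latest valid value before the first dose. Protocol Tables 1 and 2 schedule both scores at screening (Day -28 to -1) and again on Day 1.

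**The concern.** Stratified randomization balances the stratum between arms. If the stratum predicts outcome and the model leaves it out, the estimate keeps the benefit of that balance but the model-based standard error does not show it. The reported SE is then somewhat too large and the test somewhat conservative. The question is how much of this remains once continuous baseline is in the model.

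There is also a point of presentation. As written, the primary analysis reflects the randomization less fully than the continuous secondary analyses, without explanation.

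**Working it through.** **1. The plan's own figures.** From SAP 2.3: SD 5, effect 3.0, 36 per arm; SD 2, effect 1.0, 51 per arm; two-sided alpha 0.10. With SE = SD × √(2/n) and minimum detectable difference = t × SE:

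- Population #1: SE = 5 × √(2/36) = 1.1785; 1.6669 × 1.1785 = 1.964 (stated 2.0); t-test power 80.95%.
- Population #2: SE = 2 × √(2/51) = 0.3961; 1.6602 × 0.3961 = 0.658 (stated 0.66); t-test power 80.6%.

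Both reproduce.

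**2. Cost of one more parameter at an unchanged SE.** Population #1: df 69 to 68, power 80.94% to 80.93%. Population #2: df 99 to 98, power 80.59% to 80.58%.

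**3. Where the overlap is incomplete.** The stratum uses the screening score and the covariate is normally the Day 1 score, so the two need not agree. Modified ESSDAI adds a second gap. Its covariate drops the pulmonary, peripheral nervous and central nervous system domains, which Protocol 5.1.1 still scores at screening. By SAP Table 2, "Domain score = Activity level × Domain weight". Hence:

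- one level-1 pulmonary or peripheral nervous system item: 1 × 5 = 5 points;
- lowest non-zero central nervous system score: 2 × 5 = 10 points.

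A subject with the entry minimum of 5 from the other nine domains and one level-1 pulmonary item has a total of 5 + 5 = 10. That is the upper stratum, while the covariate reads 5 if nothing changes by Day 1.

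**4. Continuous models with and without the stratum, same simulated trials.** N, SD and effect are from SAP 2.3. The documents give no block size, score distributions or correlations. These are assumptions: blocks of 4 within strata, screening-Day 1 correlation mostly 0.6 to 0.9, and a range of baseline-outcome relations.

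The first check is a worst case under the null: Day 169 ANCOVA, 40,000 trials, slope of change on baseline -0.4, and an extra stratum effect beyond baseline of -2.0 (Population #1, correlation 0.7) or -0.6 (Population #2, correlation 0.6).

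| Population, model | Rejection (nominal 10%) | Mean SE | Sampling SD | SE/SD |
|---|---|---|---|---|
| #1, neither term | 7.3% | 1.1771 | 1.0834 | 1.086 |
| #1, baseline | 9.5% | 1.0437 | 1.0303 | 1.013 |
| #1, baseline + stratum | 9.9% | 1.0281 | 1.0272 | 1.001 |
| #2, neither term | 8.7% | 0.3954 | 0.3817 | 1.036 |
| #2, baseline | 9.5% | 0.3797 | 0.3758 | 1.010 |
| #2, baseline + stratum | 9.7% | 0.3769 | 0.3754 | 1.004 |

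Continuous baseline removes most of the mismatch and the stratum removes most of the rest. The mean estimate was within 0.001 of zero in every row, and adding the stratum moved the sampling SD by only -0.3% and -0.1%.

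Effect of adding the stratum across scenarios:

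| Analysis | SE change | Power change (points) |
|---|---|---|
| ANCOVA, extra stratum effect 0 or as above, Population #1 | -1.5% to +0.5% | -0.4 to +0.8 |
| Same, Population #2 | -0.8% to +0.3% | -0.4 to +0.5 |
| ANCOVA, 60 scenarios without a step at the cut | -3.3% to +0.4% | -0.6 to +1.9 |
| Of these, correlation 0.8 only | -1.1% to +0.3% | -0.6 to +0.8 |
| AUC | -4.0% to +0.4% | -0.5 to +2.4 |
| Sensitivity MMRM, worst-score imputation | -1.6% to +0.3% | -0.6 to +1.2 |
| Sensitivity MMRM, all data | -1.9% to +0.3% | -0.7 to +1.0 |
| Modified ESSDAI | -2.2% to +0.3% | -0.6 to +0.9 |

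The largest Day 169 case was Population #2 with both correlations at 0.6: SE 0.389 to 0.377, power 81.2% to 83.2%.

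Full six-visit MMRM runs (unstructured covariance, 15% of subjects with later visits excluded) agree. At screening-Day 1 correlation 0.6, 0.8 and 0.9:

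- Population #1: SE 1.180 to 1.159, 1.192 to 1.187, 1.196 to 1.200; power +1.8, -0.2, -0.4 points.
- Population #2: SE 0.404 to 0.397, 0.407 to 0.405, 0.409 to 0.410; power +0.7, 0.0, -0.3 points.

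The Monte Carlo SE of these power differences is 0.4 to 0.5 points.

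**5. Modified ESSDAI.** Here 15% or 30% of subjects were assumed to have 5 or 10 points from the dropped domains, unrelated to change in the other nine. The Day 1 covariate then explains 8% to 36% of the stratum's variance, against 23% to 49% for total baseline. The stratum is less redundant, but the precision gain is no larger.

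**The case against.** The strongest reply is that the SAP follows a sensible pattern. The stratum appears where the baseline covariate is a different instrument (FACIT-Fatigue, OSDI, PGIS, and ESSPRI in Population #1). It is absent where the covariate is the stratifying score itself. This explains the primary, sensitivity, AUC and responder models. It stands, and it leaves little inconsistency. It does not fully cover modified ESSDAI, or the gap between screening and Day 1.

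Three stronger readings are tempting, and none is supported:

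- **That SAP 3.5.2.2 contradicts itself.** After listing the stratum it says "The details of these analyses and presentations of results will be the same as those described for the primary endpoints in section 3.5.1.2". A reader might take this to cancel the list. The natural reference is to the LSMeans, intervals, displays and model checks described in 3.5.1.2, and an explicit list in the same section governs.
- **That the primary analysis is invalid or loses real power.** Simulation shows no bias and a rejection rate at or slightly below nominal. The sign of the power change is not fixed. Gains near 2 points need a weak screening-Day 1 correlation, which the documents neither state nor suggest.
- **That the responder models need the same change.** There the stratum brought no precision gain: the SE of the log odds ratio rose by 0.7% to about 5% across assumed settings, and the odds ratio becomes conditional on the stratum.

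It is also fair to say that the modified-ESSDAI analysis is only supplementary.

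**Conclusion.** The omission is real but minor. It is a free improvement not taken, not an error. Continuous baseline already recovers most of what the stratum offers, so the treatment estimate hardly moves.

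Adding the stratum would change the SE by about +0.5% to -1.5%, reaching about -3% for the Day 169 analysis (-4% for AUC) only at the edge of the assumed range. Power would usually move by less than 1 point, at most about +2. The sample sizes of 72 and 102 are unaffected. The real gain is an SE that follows the design a little more closely where the baseline-only model is slightly conservative.

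That there is no bias and no type I inflation held in every setting tried. The sizes rest on assumed correlations, score distributions and block size.

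**What to change.** Before the first unblinding (the Day 85 interim analysis), add the randomization stratification factor, as recorded in the IXRS, as a fixed effect in:

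- the primary MMRMs for both populations (SAP 3.5.1.2);
- the rescue-handling sensitivity models and the AUC model (SAP 3.5.1.5);
- the modified-ESSDAI models and the Stage II primary-score models (SAP 3.5.1.8).

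Keep continuous baseline in all of them, and leave the responder logistic models unchanged. One sentence saying that those models already carry the continuous stratifying score would explain the remaining difference.

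The cost is SAP wording, one parameter per model and at most about 0.5% in SE, with no new data. The documents do not show whether the interim unblinding has taken place. If it has, changing the primary model is no longer a near-free edit.
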